4.10 Study Definition of Completion

Participant study completion will be defined as a participant who has been enrolled and completes Visit 3.

5. STUDY POPULATION

5.1. Selection of the Study Population

Children 8 to 17 years of age with obesity (BMI \geq 95th percentile for age and sex) being seen for a visit at the Duke HL clinic, and meeting study inclusion and exclusion criteria will be enrolled. Both males and females are eligible, as are participants of any race or ethnicity. Participants (or parent/guardian) must have access to the internet and an approved device/computer (see below).

5.2. Inclusion/Exclusion Criteria

Inclusion Criteria	
1. Documented informed consent from legal guardian and assent from participant as appropriate.2. Children 8 to 17 years of age with obesity (BMI \geq 95th percentile for age and sex) being seen at Duke Healthy Lifestyles clinic.3. Participants (or parent/guardian) must have access to the internet and an approved smart device/computer.4. Child must have a designated caregiver who expresses a commitment to encourage the participant to complete the study procedures.5. Participant and legal guardian must speak and read English or Spanish.
Exclusion Criteria	
1. Prior enrollment in an IMR program.2. Contraindications for IMR including a history of recent lung surgery, recent pulmonary embolism, or history of recurrent spontaneous pneumothorax3. Progressive neurological or neuromuscular disorders or need for chronic O₂ therapy.4. Inability to complete baseline measurements in a satisfactory manner according to the judgment of the research coordinator or PI.5. Body weight greater than 300 pounds.6. Any condition in the opinion of the PI that would not allow safe conduct of study procedures (including IMR, MIP testing or step-test), such as a physical disability, recent musculoskeletal injury or illness, current and ongoing evaluation for undiagnosed cardiopulmonary or neurologic symptoms, undiagnosed chest pain, pneumothorax in the past 12 months, inner ear surgery in the past 12 months, or undiagnosed syncopal episodes.

5.3. Screen Failures

Participants who sign informed consent but are not enrolled in the active study are considered screen failures and will be recorded in the Screen Failures area of the electronic data capture (EDC). Participants who do not initially satisfy eligibility requirements may be rescreened up to 2 additional times. Re-consent is not required for rescreened participants unless a revised version of the consent that requires re-consent is made available.

5.4. Treatment Assignment Procedures

5.4.1 Randomization procedures

Treatment assignment will be 1:1 (IMR or sham intervention), and will be obtained through the Duke REDCap randomization system using the randomization schedule as

designed by the unblinded statistician. All study staff and participants will be blinded to the treatment assignment with the exception of one un-blinded clinical research coordinator. Participants may be able to tell whether their device is set to the active resistance. Although complete masking may not be possible in all participants, participants will only be informed that they are receiving one of two resistances (low or active). However, all study staff that assess outcomes (and the lead statistician) will remain blinded. Participants will be instructed to not discuss their presumed IMR assignment with study staff.

5.5. Participant Discontinuation/Withdrawal

5.5.1 Participant decides to withdraw consent

A participant may voluntarily withdraw consent to participate in the study at any time. Participants are not obligated to state the reason for withdrawal. Participant withdrawal should not affect the participant's medical care outside of this study. The reasons for withdrawal, or failure to provide a reason, must be documented by the investigator. No additional study procedures or data should be collected after consent has been withdrawn.

5.5.2 Participant decides to withdraw from study intervention/product

Participants may also withdraw from receiving the study intervention/product for any reason but continue to be followed for safety. Participants are not obligated to state the reason for withdrawal.

5.5.3 Study investigator/sponsor decides to withdraw participant

The study investigators or sponsor may decide to take the participant out of this study at any time without consent if:

- Participant's condition changes and the study is no longer in his/her best interest;
- Participant non-compliance with the study protocol;
- The entire study is stopped by the sponsor.

5.5.4 Individual stopping of dosing criteria:

The study investigators will stop treatment of study intervention and the participant will not receive additional doses of study intervention if:

- Participant has a clinically significant severe AE or SAE related to the study intervention;
- Participant becomes pregnant;
- Participant newly meets criteria for study exclusion;
- In the opinion of the investigator, the participant is at significant risk.

If the intervention is discontinued for safety concerns, participants must be followed for safety until 7 days after the last study training session. Participants who are discontinued from study intervention due to an AE, whether serious or non-serious, must be followed by the investigator until the AE is resolved or considered stable.

If any of the above occurs, the participant will be informed, and the investigator will discuss other options.

5.5.5 Handling of withdrawals

The reasons for withdrawal, or failure to provide a reason, must be documented by the investigator. Reasons for withdrawal may include:

- a. Participant withdraws consent and requests no further follow-up;
- b. Participant does not withdraw consent but withdraws from study intervention;
- c. Study PI/Sponsor decision.

Unless there is complete withdrawal of consent from the participant, every effort will be made to continue follow-up visits.

5.5.6 Replacements

Females who become pregnant during the study will not receive further study intervention. In cases of early withdrawal, an additional participant may be enrolled.

6. STUDY PROCEDURES

Procedures will occur as in

Table 4.

6.1 Screening

The investigator will screen participants in accordance with the eligibility criteria detailed previously. Research staff will document applicable informed consent for all participants who satisfy eligibility criteria, and will follow all site policies, procedures and criteria for control of COVID-19.

Participants must satisfy all Inclusion/Exclusion criteria to be enrolled in the active study. Information will be recorded from the clinical medical record or from interview of the participant. The investigator will not exercise selectivity so that bias is prevented.

Table 4 Study Procedures

	Screen visit	Randomization visit	Completion visit
Visit number	V1	V2	V3
Timeline in days (target)	-10-14 ^a	0	42 (40-56)
Consent/assent	x		
Height/Weight/BMI [#]	x		x
Eligibility assessment	x	x ⁵	
Study instructions	x	x	
Actigraphy training ¹	x	x	
PrO2 device/app training		x	
Retrospective Dyspnea scoring ^{##}		x	x
Dyspnea scoring with exercise ²		x	x
Randomization		x	
Maximal inspiratory pressure (MIP) ^{###}		x	x
Stair Step Test		x	x
Adverse event monitoring		x	x
Follow-up actigraphy ³			x
Patient satisfaction questionnaire			x
phone check-ins ⁴	will occur on day (+/- 2) 7, 14, 21, 28, and 35 to assess any problems, encourage adherence and give appreciation for efforts		

1 – worn at least 7 full days (max of 14) prior to randomization

2 – Modified Borg Dyspnea scale and Dalhousie Dyspnea

3 – worn at least 7 full days (max of 14) during week prior to V3; the follow-up actigraphy should occur during the last 14 days.

4 – communication will be made by (IRB approved) mode of participant's choosing including voice call or direct messaging.

5 – assess for eligibility for randomization (tracker adherence, no new exclusions prior to randomization)

a – a date range of 10-14 days prior to randomization is preferred but can be extended up to -28 days. A randomization visit can be scheduled beyond 28 days only at the discretion of the PI.

- should be taken from clinic visit data; may be performed as a research procedure only if needed

- Baseline Dyspnea index (BDI) and MRC Breathlessness Scale

- MIP will be collected before and after the Stair step test

Informed consent and collection of demographic information will be performed at screening. The following screening assessments must be done to confirm study eligibility: medical history (past medical/surgical history, medications, and smoking/drug history), review of concomitant medications, height/weight/physical exam, and confirm satisfaction of all eligibility criteria (inclusion and exclusion) for the study. Assessments not recorded per standard of care, must be conducted as a study specific procedure.

6.2 Summary of Procedures

6.2.1 Visit 1 (goal timing: day -10 to -14 prior to randomization)

General Visit Description: Eligibility criteria will be confirmed at Visit 1 or via phone call before their visit to the Healthy lifestyle's clinic, if the researcher believes the participant meets eligibility criteria. Research staff will document informed consent from the parent/ guardian in eligible participants.

Participants above the age of 12 years will also provide assent. Eligible participants will receive a Breathe Fit study packet with study handouts and study materials.

Equipment/Supplies needed: Body weight scale, stadiometer, eligibility checklist (printed or electronic), participant informational handouts (for activity tracker accompanying smart device(s) to link with activity tracker).

Anticipated duration: Goal is 30-45 minutes.

Visit 1 Procedures:

1. Confirm eligibility (eligibility checklist).
2. Obtain consent and assent (if child is <12 years old). The consenting process will include instruction about general study details (visits, durations, compensation) and participants will be given a study packet of instructions.
3. Obtain participant demographics, including height, weight, and BMI data (these data should be taken from the electronic health record if already collected). If not obtained during routine care, these data will be collected by research staff.
4. Questionnaires (printed or electronic).
5. Actigraphy training (participants will be given a Vivosmart 4 activity tracker in the correct size and taught on its proper fit and use).
6. Following consent, if all V1 procedures are not able to be completed (due to participant time constraints or family preference), an optional V1a (continuation visit) may be scheduled by phone or in-person home or by follow-up clinic visit.
7. Plan day -7 phone check-in (see phone check-in section below).

6.2.2 Visit 2 (Day 0)

General Visit Description: Visit 2 will be Day 0, will re-confirm eligibility prior to randomization, will include randomization if eligible and will start the intervention and observation period. Participants must not newly meet any exclusion criteria and must continue to meet all inclusion criteria. Inclusion criteria for randomization will include collection of at least 7 days of valid actigraphy data (confirmed at Visit 2).

Equipment/Supplies needed: Activity tracker (from participant), accompanying smart device(s), printed questionnaires, participant informational handouts, PrO2 trainer, Stair Step Test equipment.

Anticipated duration: 60 minutes.

Visit 2 Procedures:

1. Assessment of baseline actigraphy (participants must have worn the Vivosmart 4 activity tracker for at least 7 full days (max of 14) prior to randomization. If not,

the date of Visit 2 may be extended for an additional 4-14 days for a continuation Visit 2).

2. Questionnaires and eligibility assessment (eligibility checklist, questionnaires can be printed or electronic) (see questionnaires section).
3. Interval history and event monitoring.
4. Measure Maximal inspiratory pressure (MIP) before and after step test (see MIP section).
5. Stair Step Test (see stair step section).
6. Retrospective dyspnea scoring that assesses dyspnea from daily activities (Baseline Dyspnea Index (BDI), the MRC Breathlessness scale), and during the step-test (Modified Borg Dyspnea scale and Dalhousie Dyspnea/Perceived Exertion Scale).
7. Randomization (see the randomization procedure section).
8. Study instruction refresher and questions/answers.
9. PrO2 Fit app and device IMR training.
10. Refresher Training (question and answers) on the use of Vivosmart 4 activity tracker.
11. Discuss plan for phone call visits and future study visit. Plan next phone call check-in visit (Day 7).

6.2.3 Continuation visit

In the event that during the initiation of Visit 1, 2, or 3, the participant is not able to complete the visit (but remains eligible for study participation), a continuation visit (e.g. 1b, 2b) can be scheduled to finish protocol-defined procedures. The continuation visit will be scheduled at the earliest possible date but no later than 14 days from the previous visit. The continuation visits beyond 14 days out of this window must be approved by the study PI.

6.2.4 Home visit

Conducting all or part of a planned visit is allowed but will only be conducted as a last option, is requested by the participant and legal guardian, and meets all home visit requirements. The home visit must be approved in advance by the PI and deemed to be an appropriate setting (adequate space available, approved by participant's legal guardian, safe environment). Home visits will occur only when two or more IRB-approved study staff members are present and occurring during normal business hours.

6.2.5 Phone check-ins (days -7, 7, 14, 21, 28, and 35)

During phone check-ins, communication will be made by a (IRB approved) mode of participant's choosing including voice-only or zoom call. Research staff will ask if there are any problems, concerns or questions about the study or intervention. Study staff will encourage adherence, and give appreciation for the participant's efforts.

6.2.3 Visit 3 (Day 42) Final In-person visit

General Visit Description: Visit 3 will be on approximately day 42, final assessment of the study. This visit is preferred as an in-person study visit, but may be conducted as an in-home visit if needed (as with Visit 2). Day 42 (+/- 5 days) will be the goal day for study Visit 3. With PI approval, Visit 3 may be conducted up to 14 days away from Day 42, if necessary.

Equipment/Supplies needed: Scale, stadiometer, activity tracker (from participant), accompanying smart device(s), printed questionnaires (or tablet-based REDCap questionnaires), PrO2 trainer (from participant), Stair Step Test equipment, assignment and thank you letter.

Anticipated duration: 60 minutes.

Visit 3 Procedures:

1. Reassessment of participant height, weight, and BMI.
2. Dyspnea scoring assessing daily activities [Baseline Dyspnea Index (BDI), the MRC Breathlessness scale].
3. Dyspnea scoring during the step-test (Modified Borg Dyspnea scale and Dalhousie Dyspnea and Perceived Exertion Scale).
4. Adverse effect monitoring.
5. Measure Maximal inspiratory pressure (MIP) before and after step test.
6. Stair Step Test.
7. Follow up actigraphy (participants must have worn the Vivosmart 4 activity tracker for at least 7 full days (max of 10) during week prior to Visit 3).
8. Patient satisfaction questionnaire.
9. Close out procedures:
 - i. Assignment envelope;
 - ii. Close out letter (i.e. thank you letter).

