4.1 Randomization

Participants (n=30) will be randomized to one of two treatment arms.

- Arm A (n=15): IMR
- Arm B (n=15): Sham

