Figure 3 Change in validated asthma symptom scores with IMR. ACT – asthma control test, ACQ6 – asthma control questionnaire 6 item

75% MIP three days per week. Preliminary IMR findings from 11 participants involving changes in respiratory muscle strength and endurance, 6-minute walk distance and asthma symptom scores are encouraging and support the aims of this proposal (See **Figure 3** and **Table 3**). Adherence of IMR (n=6) was 79.2% of prescribed repetitions over 6 weeks, which is superior to published adherence rates (47-57%) for daily asthma controller drugs.

Table 3 Effects of Daily IMR treatment over 6 weeks on Respiratory Outcomes – Preliminary data

Outcome type	Intervention		p-value	Summary
	IMR (n=6)	No IMR (n=5)		
Asthma Symptoms: change in ACT, mean (SD) (for ACT, higher score means better asthma)	+1.0 (0)	-3.0 (2)	p=0.075	IMR-treated participants showed a near significant improvement in ACT compared to controls (Figure 3)
Asthma Symptoms: change in ACQ-6, Mean (SD) (for ACQ-6, lower score means better asthma)	-0.10 (0.56)	0.90 (0.90)	p=0.094	IMR-treated participants showed a near significant improvement in ACQ-6 compared to control (Figure 3)
Inspiratory muscle strength: change in baseline MIP (cm H ₂ O), mean (SD)**	+37.0 (24.1) ¹	+12.5 (16.4) ¹	p=0.128	IMR-treated participants showed near significant greater MIP improvement compared to controls
Inspiratory muscle strength: change in post-exercise MIP (cm H ₂ O), mean (SD)**	+14.6 (10.5) ²	-19.0 (19.9) ²	p=0.014	IMR-treated participants showed a significantly greater post-exercise MIP improvement compared to controls
Exercise tolerance: improvement in six-minute walk distance (meters), mean (SD)	119.1 (93.3)	4.0 (112.7)	p=0.136	IMR-treated participants showed non-significant improvement in

				6MW distance compared to controls
**two MIP measures were analyzed at each visit because of acute strengthening. ¹ – MIP1 start of visit (before exercise), ² – MIP2 end of visit (after exercise). ACQ-6 – score ranges from 0 to 6 with lower score meaning better asthma. Minimal important difference =0.4-0.5. ACT – score ranges from 6 to 30 with higher score meaning better asthma. Minimal important difference = 3				

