7.1.3 Product use and directions

Participants will be instructed to inspire forcefully through PrO2™ until the device signals that the user has achieved the target resistance (via audible alarm and visible light signal). The research team can implement biofeedback signals at a specific inspiratory resistance, which allows for a precise and individualized training target.

At Visit 1: Participants will download the PrO2™ Fit App from the Apple App Store or Google Play. They will be shown how to set up their own PrO2 Fit account and how to connect with their PrO2™ trainer. Research staff will review the planned dosing to start after visit 2. They will be instructed to try to avoid inferring what treatment assignment they have been given, and to not share any impressions they have developed on treatment assignment. The proper use of the trainer will be taught, including safe storage, cleaning and maintenance. Participants will be taught to create an air-tight seal over the mouthpiece after maximal exhalation. The participant will be instructed to breathe in forcefully until the device alarms then continue to maximal inspiration. At Visit 1, participants will be taught on the device while the alarm is set for 15% of their MIP. They will complete a set of 50 repetitions supervised so their technique is assessed and re-direction can occur if needed.

At Visit 2: participants will have refresher training on the use of the PrO2™ Fit app and will repeat their supervised single set of 50 repetitions while supervised to ensure they have the proper technique and the device is working properly.

Research staff will encourage participant and guardian to discuss a plan to optimize adherence to the IMR intervention. This may include picking particular days of the week (e.g. MWF, TuThS) and particular activities to link with IMR (e.g. in mornings before school, evenings before homework, etc.). Guardians will be asked to commit to helping the participant remember their intervention days.

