10.7 General Summary of Study Data

Statistical analyses will be overseen by [name], a faculty member within the Department of Biostatistics & Bioinformatics at Duke. She will serve as the unblinded statistician and oversee the lead statistician.

Patient disposition, demographics, baseline measurements, outcomes and adverse events will be summarized overall and by intervention group. We will use standard summary statistics to describe the distribution of outcome measures outlined in each aim by intervention group including mean, standard deviation (SD), median, 25th and 75th percentiles (Q1-Q3) and range for continuous variables and frequency counts with percentages for non-missing data. We will assess distribution and normality assumptions, identify outliers, evaluate missing data and check for unusual patterns. We will use SAS version 9.4 or higher (SAS Institute, Inc., Cary NC) for all analyses, and a two-sided p-value <0.05 will be considered statistically significant. Data derivations, calculations and analysis programs will be archived to allow future replication of our results.

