10.10 Efficacy Analyses

Aim 1: We will use exact 95% confidence intervals and Fisher's exact test to report and compare the expected satisfaction, adherence and SAE percentages within the IMR compared to the sham group.

Aim 2: We will use analysis of covariance (ANCOVA) to estimate and test the difference in mean 6-week change between treatment groups (IMR versus Sham) for each outcome adjusting for the baseline value of the outcome variable. Given the small sample size, sex (male/female), age, and BMI will each be evaluated in separate ANCOVA models. We will report adjusted (least squares) means with 95% confidence intervals (CI) for each group, as well as the estimated between-group difference in means with 95% CI and p-value for testing the null hypothesis of no difference between group means. The model assumptions will be verified for each outcome, and model fit will be assessed using residual plots.

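### Visit 3 MIP and step tests are not kept apart from home training, so an acute effect that differs by arm could enter the 6-week comparison

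*Combined protocol and SAP*

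**What the plan says.** **Visit 2 (section 6.2.2).** Item 4 is "Measure Maximal inspiratory pressure (MIP) before and after step test (see MIP section", item 5 the step test, item 7 randomisation and item 9 device training. Section 7.1.3 has assigned dosing start after this visit. Targets are percentages of the child's own MIP (sections 4.3 and 7.1.1), so MIP must be known before the first assigned session.

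**Visit 3 (section 6.2.3, Day 42).** The instruction is "Measure Maximal inspiratory pressure (MIP) before and after step test". Neither this section, Table 4 nor the MIP procedure in section 6.5 sets an interval since the last home session or asks for it to be recorded.

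**Home training.** Both arms train three times a week. Families choose the days and times; the examples in section 7.1.3 include "in mornings before school, evenings before homework". The text does not say whether training continues until Visit 3 when that visit is later than Day 42.

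**Acute change in MIP.** The footnote to Table 3 (section 4.8) explains that in the pilot "two MIP measures were analyzed at each visit because of acute strengthening".

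**Analysis (section 10.10).** ANCOVA of the 6-week change, "adjusting for the baseline value of the outcome variable", with sex, age and BMI examined in separate models. Time since the last session is not a term.

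**The concern.** The 6-week changes are meant to show adaptation to training. The baseline tests come before any assigned session. The final tests may come a few hours after one, which is 150 breaths at a 75% target in one arm and at a 15% target in the other. If a session leaves a short-lived effect on the inspiratory muscles, whether strengthening or fatigue, and that effect depends on load, it would be present only at Visit 3 and would differ by arm.

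Randomisation does not balance such an effect, because it arises after randomisation and from the assigned load. Adjusting for baseline does not remove it either. The outcomes at stake are the MIP change (secondary) and possibly two step-test measures: heart rate (exploratory) and dyspnea during the test, which section 10.1 names in a secondary hypothesis although Table 1 does not list it. Satisfaction, adherence and completion are untouched.

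**Working it through.** **1. The plan's own figure.** Inputs: 30 children ("Participants (n=30) will be randomized to one of two treatment arms", section 4.1), equal allocation (section 5.4.1), and "a two-sided p-value <0.05 will be considered statistically significant" (section 10.7). Power comes from a two-sample t-test with a noncentral t distribution, df = N - 2, and noncentrality d / sqrt(1/n1 + 1/n2). For d = 0.95 and 15 per arm, the noncentrality is 0.95 / sqrt(2/15) = 2.60 and power is 0.7094; Table 5 gives 0.709. All 24 cells reproduce within 0.001. Table 5 is correct and serves below only as a reference.

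**2. How many children could be affected.** With three training days in seven, and a visit day unrelated to them, 3/7 = 0.43 of visits fall on a training day, and 0.43 × 15 = 6.4 children per arm. This is a ceiling under those assumptions: it takes training to be still running at Visit 3 and counts every training-day visit, including those where the session would come in the evening.

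**3. What Table 3 does and does not show (n = 6 IMR, n = 5 no IMR).**

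| 6-week change in MIP, cmH2O | IMR | No IMR | Difference |
|---|---|---|---|
| Before exercise | +37.0 | +12.5 | 24.5 |
| After exercise | +14.6 | -19.0 | 33.6 |
| Gap (before minus after) | 22.4 | 31.5 | -9.1 |

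Only a shift that differs between arms can move the treatment contrast. Here it is 33.6 - 24.5 = 9.1 cmH2O. The larger within-arm gap is in the controls. Each gap is also a difference of differences: if the same children contribute to both rows, the post-exercise change minus the pre-exercise change equals the within-visit response at the last visit minus that at baseline. The table therefore shows that the between-arm result is sensitive to muscle state. The stimulus was exercise at the same visit, so it does not measure carry-over from a training session.

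**4. Possible bias under stated assumptions.** Let f be the share tested within the carry-over period and a the active-minus-sham acute effect on MIP. Then bias = f × a. The pooled SD of the pre-exercise change in Table 3 is sqrt((5 × 24.1² + 4 × 16.4²) / 9) = 21.0 cmH2O. The values of a are assumptions, because the documents give none. The small extra spread from mixing affected and unaffected children is ignored.

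| f | a (cmH2O) | Bias (cmH2O) | Bias / SD | Rejection rate, no lasting effect, N = 30 | Power at true d = 0.95, N = 30 |
|---|---|---|---|---|---|
| 0 | any | 0 | 0 | 0.050 | 0.709 |
| 3/7 | -10 | -4.3 | -0.20 | 0.084 | 0.505 |
| 3/7 | -5 | -2.1 | -0.10 | 0.058 | 0.611 |
| 3/7 | +5 | +2.1 | +0.10 | 0.058 | 0.794 |
| 3/7 | +10 | +4.3 | +0.20 | 0.084 | 0.862 |
| 3/7 | +15 | +6.4 | +0.31 | 0.128 | 0.913 |

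Halving the exposure to 3/14 with a = ±10 gives the ±5 rows, since 3/14 × 10 = 2.1. Putting the 9.1 cmH2O from Table 3 in place of a, purely as a yardstick, gives 3/7 × 9.1 = 3.9 cmH2O. The documents hold no figure for an acute effect on step-test heart rate or dyspnea, so none is computed.

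**The case against.** The strongest reply is that the carry-over is unproven. Nothing in the documents shows that an acute change in MIP lasts for hours, that it differs between 75% and 15% loads, or that it reaches step-test heart rate or dyspnea. That stands, and it limits the point to a plausible risk.

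A reader might infer from Table 3 that acute shifts of 22.4 and 31.5 cmH2O rival the 24.5 cmH2O treatment difference, or that the active arm must carry the larger effect. The table supports neither. Those are within-arm gaps after exercise in 11 children, only their 9.1 cmH2O difference bears on the contrast, and the larger gap is in the controls.

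The exposure may also be small. Evening sessions would normally follow a daytime visit, and training might stop at Day 42. That too stands, and is why 3/7 is treated as a ceiling.

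The protocol does recognise acute change. It measures MIP before and after the step test at both visits, and section 6.5 asks for five manoeuvres with the best two within 10 cmH2O. This controls conditions within the visit and repeatability, but not what the child did that morning.

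Finally, this is a 30-child pilot with descriptive primary endpoints, and an instruction may exist elsewhere: section 12.7 refers to a manual of procedures, and the study schematic is not visible in the public text. These are reasons to keep the point modest. They do not close the gap in the protocol.

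**Conclusion.** The asymmetry is in the documents. Visit 2 tests are listed before the first assigned session, Visit 3 tests may follow a session by hours, and the planned ANCOVA cannot remove an acute effect that differs by arm. Such an effect could be mixed into the 6-week MIP change and possibly into the step-test outcomes.

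It would go too far to say that the MIP estimate is biased: size, sign and persistence are all unknown. With at most 3/7 of children affected and an assumed acute difference of -10 to +15 cmH2O, the bias is -4.3 to +6.4 cmH2O (-0.20 to +0.31 SD), well below the pilot difference of 24.5 cmH2O. At N = 30 the false-positive rate would be at most 0.128, and power at d = 0.95 would lie between 0.505 and 0.913 instead of 0.709. These figures rest on the assumed effect, on training continuing up to Visit 3, on a visit day unrelated to training days, and on an SD from 11 pilot children.

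The point is worth acting on because prevention costs almost nothing and the timing of the test cannot be corrected afterwards.

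**What to change.** In section 6.2.3 (Visit 3), state that the visit is booked on a day when the child is not due to train, and add a reminder to the day-35 check-in. Three sessions a week leave four such days in every seven, so load, repetitions and weekly frequency need no change. Moving that day's session to after the visit is not a good alternative, because it would follow close-out, when the assignment envelope is given, and might fall outside the period over which adherence is counted.

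At Visit 3, record the date and time of the last session. Section 4.3 says that all repetitions are captured automatically; whether the app log holds clock times should be confirmed, and if it does not, the child or guardian can be asked.

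In section 10.10, add a sensitivity analysis of MIP and the step-test outcomes by same-day training, labelled as conditioning on post-randomisation behaviour. It should not replace the main analysis: at the 3/7 ceiling, leaving out same-day trainers would keep only about 15 - 6.4 = 8.6 children per arm.

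The cost is one sentence in the visit section, one line in the check-in script, one recorded item, one extra analysis, and slightly less freedom in booking Visit 3.
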